Furthermore, adiponectin, leptin, insulin. Markers of the renin-angiotensin-aldosterone system. Organ-specific antibodies, including TPO antibody, transglutaminase antibody IgA, total IgA, deamidated gliadin peptide antibody IgG, and markers of immune system activity, including high resolution CRP and immunoglobulins.

Furthermore, selected inflammatory and pro-inflammatory markers as well as adipokines. DNA is taken from leukocytes for genetic studies, see below.

Flow cytometry will be performed on fresh blood at the Department of Clinical Immunology, Aarhus University hospital, where lymphocyte subpopulations and cell differentiation will be examined. In cell culture studies, dendritic cells and their co-stimulatory factors will be examined. In addition, measurement of soluble HLA-G as well as functional studies of the regulatory T cells' suppressor function will be performed.

Surveys

A sub-cohort of 100 test subjects will complete the study program below, see figure 2. Separate information material has been prepared for this, see appendix 5.

Baseline examinations will be carried out within 14 days of referral.

Examinations at three and nine months will be carried out with a precision of +/- four weeks.

The examinations (including biopsies) will be repeated in connection with the end-of-study blood test after a renewed information interview and informed consent. Only participants who have previously participated in this research program and who continue to participate in the DAGMAR study will be able to participate. Pregnancy is an exclusion criterion. The background for the repeated examinations is that at the nine month investigations, especially the muscle strength testing, there are signs of continued improvement. Long-term clinical studies in Graves' disease on these aspects are currently limited or non-existent. It is therefore unclear when final restitution will be achieved, which these studies will be able to help shed light on.

Osteodensitometry

Bone scans will be performed as a "Dual-Energy X-ray absorptiometry" (DEXA) scan with a Hologic QDR Discovery scanner. BMC and BMD will be measured in the lumbar spine (L1-L4), the hip region (femoral neck, trochanter, Ward's triangle and intertrochanteric region), the forearm (proximal, middle 1/3 and ultra-distal) and the whole body. Furthermore, body composition will be determined.

HRpQCT scan

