From both written and oral information, it will appear that this is a scientific experiment. The design of the survey will be carefully reviewed. The project's purpose, potential risks and discomfort as well as expected benefits will also be stated. Furthermore, the participant will be made aware that there may be unpredictable risks and burdens linked to participation in a biomedical research project. It will be emphasized that participation is voluntary and that the person has the right to withdraw their commitment to participate in the study at any time without further justification and without this affecting the rest of the treatment at the hospital.

The project participant will be informed of the right to reflection time ("can go home and think about things") before giving a final answer. If the person concerned wishes to participate in the study, the person concerned can give oral and written consent to this at the end of the interview. If the patient asks for time to think, the person is requested to give feedback within 2 weeks, in the event that the person decides to participate in the study. In that case, a new time will be agreed for a repeated information interview under a similarly undisturbed framework and with the possibility of co-sitters. Verbal and written consent to participate in the study will then be obtained. The project participant receives a copy of this.

After obtaining consent, the investigator will inform each subject's general practitioner that he or she is participating in the study.

Especially regarding the controlled cohort study ii)

Purpose

Examining the muscle balance function in patients with newly diagnosed Graves' disease, etc. to clarify whether this has normalized three months after starting anti-thyroid treatment.

Hypothesis.

Muscle and balance function in newly diagnosed patients with Graves' disease will be reduced compared to healthy sex- and age-matched controls.

Three months after starting anti-thyroid treatment, there is no longer a difference between controls and the patients who have received vitamin D supplementation, whereas patients who have not received vitamin D supplementation continue to have reduced muscle and balance function compared to the controls.

Design

Controlled prospective cohort study of patients with newly diagnosed Graves' disease vs healthy sex- and age-matched controls.

Population

Fifty-five healthy controls, matched for sex and age (+/- 2 years) and menopause status.

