Inclusion criteria

- Between 18 and 80 years old
- Euthyroidism
- Speaks and reads Danish
- Written consent after oral and written information

Exclusion criteria

- Current or previous metabolic disease
- Significant other disease, including renal impairment (eGFR <60 ml/min, hypercalcemia, treatment with the glucocorticoid system.
- Known neuromuscular disorders
- Pregnancy
- Alcohol abuse resulting in the need for treatment or hospitalization
- Abuse of euphoric substances

Statistics/strength calculation

In our research group, in a previous study on healthy adults, we have found that the mean value for maximum knee flexion at 90 degrees is 463N with a standard deviation of 170 N. To detect a difference between groups of 20% with a power of 0, 80 given a significance level of 0.05, 53 participants are required in each group.

During thyrotoxicosis, the loss of bone mass has been estimated at 9% per remodeling cycle. Assuming that the average lumbar bone mass density is 0.92 g/cm² (SD 0.11 g/cm²), with the

stated population size we will be able to demonstrate a difference between groups of 10% at baseline with a power of 0.97 ($\alpha=0.05$).

A recent meta-analysis found that the risk of all-cause mortality and cardiovascular death increased by 15% for an increase in pulse wave velocity (PWV) of 1 m/s. Given a standard deviation of 1.5 m/s in each group, the study size will be able to demonstrate a difference between groups at a baseline of 1 m/s with a power of 0.94 ($\alpha=0.05$).

Data collection

Survey program

The participants complete an examination program similar to the baseline examinations for the intensively examined cohort in the randomized clinical trial:

Baseline

Health information

Blood tests

Questionnaire about i.a. quality of life

DXA scan

HRpQCT scan

Arterial stiffness and blood pressure measurement

Muscle and balance function examination

Follow-up, carried out with a precision of +/-4 weeks

Blood tests

questionnaire

Muscle and balance function

Arterial stiffness and blood pressure measurement

Health information and questionnaire

Participants answer the same baseline, ThyPRO and follow-up questionnaire as approved for the main study.

Based on the interview and questionnaire, the following will be registered in the CRF:

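### Study ii asks whether muscle function has normalised at three months but sets no margin or confidence-interval criterion, so a non-significant difference is the only basis available for that conclusion

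*Combined protocol and SAP*

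**What the plan says.** All of this is in the protocol section on the controlled cohort study ii.

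- **Purpose:** to examine muscle and balance function in newly diagnosed Graves' disease and "to clarify whether this has normalized three months after starting anti-thyroid treatment".
- **Hypothesis:** function is reduced at diagnosis. At three months "there is no longer a difference between controls and the patients who have received vitamin D supplementation". In the arm without vitamin D, the plan expects the impairment to persist. The no-difference statement therefore concerns the vitamin D arm only.
- **Population:** 55 healthy controls matched on sex, age and menopause status.
- **Statistics/strength calculation:** the group's earlier data on healthy adults supply a mean of 463 N and an SD of 170 N for knee flexion at 90 degrees. The size per group is then given: "To detect a difference between groups of 20% with a power of 0, 80 given a significance level of 0.05, 53 participants are required".

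Study ii names no test of its own. The original and final statistical analysis plans, which are written around the randomised trial, name only tests of difference (two-sample t-test or a non-parametric equivalent) for continuous measures. No margin, equivalence or non-inferiority test, or definition of normalised appears in any of these places.

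**The concern.** Whether function has returned to the control level is a question about sameness. To answer it, the plan must say how large a remaining difference still counts as normal. A study powered to detect a difference answers the opposite question. If it finds none, the reason may be recovery, too few evaluable participants or noisy strength measurements. A plan that offers only the non-significant result makes a claim of normalisation easier to reach as the data become less precise.

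The timing makes this more than formal. The protocol's background on Graves' disease describes case series in which weakness kept improving for four to five months before levelling off, which is later than the three-month comparison. Under Surveys, the protocol says of the nine-month examinations that "especially the muscle strength testing, there are signs of continued improvement". Incomplete recovery at three months is therefore plausible, and study ii could report recovery in the vitamin D arm while a material deficit remains.

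**Working it through.** **Inputs from the plan.** Control mean 463 N, SD 170 N, alpha 0.05, power 0.80, difference 20% = 0.20 × 463 = 92.6 N.

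**Reproducing the plan's size.** n per group = 2 × (1.960 + 0.842)² × (170 / 92.6)² = 52.9, so 53. This matches the stated figure and shows that the test is two-sided; a one-sided test would need 42.

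**Group sizes for the hypothesis as written.** The comparison is vitamin D patients against controls.
- 50 v 55: the sub-cohort of 100 is randomised equally (Population size), giving about 50 vitamin D patients.
- 27 v 55: this assumes that only 55 individually matched patients are used and that about half received vitamin D.

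**Chance of a non-significant result.** SE = 170 × √(1/n₁ + 1/n₂), and the non-centrality is deficit / SE.
- 50 v 55: SE = 33.2 N, critical t = 1.983 (103 df). For a 10% deficit, 46.3 / 33.2 = 1.39.
- 27 v 55: SE = 39.9 N, critical t = 1.990 (80 df). For a 10% deficit, 46.3 / 39.9 = 1.16.

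| Assumed residual deficit | 50 v 55 | 27 v 55 |
|---|---|---|
| 5% (23.2 N) | 89% | 91% |
| 10% (46.3 N) | 72% | 79% |
| 15% (69.5 N) | 46% | 60% |
| 20% (92.6 N) | 21% | 37% |

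**Precision.** The 95% CI half-width is 1.983 × 33.2 = 65.9 N (14% of 463 N) at 50 v 55, and 1.990 × 39.9 = 79.5 N (17%) at 27 v 55. At 50 v 55, an observed deficit just short of significance would have an interval reaching about 2 × 65.9 = 131.8 N, or 28% below the control mean.

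**Sensitivity for a 10% deficit.** With all 100 sub-cohort patients against 55 controls the rate is 64%. With 55 matched pairs (SD of the pair difference = 170 × √(2(1 − r))) and assumed correlations of 0.2, 0.4 and 0.6 it is 65%, 56% and 40%. With 53 v 53 and an SD from 130 to 210 N it runs from 55% to 80%.

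**The margin rule.** Normalisation is concluded if the lower 95% limit for patients minus controls lies above −M. The non-centrality is (M − true deficit) / SE.

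| Margin, true deficit | 50 v 55 | 27 v 55 |
|---|---|---|
| 20%, none | 79% | 63% |
| 20%, 10% | 28% | 21% |
| 20%, 20% | 2.5% | 2.5% |
| 10%, none | 28% | 21% |

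With an assumed loss to 45 v 50, power for the 20% margin at true equality is 75%.

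**The case against.** The strongest reply is that the documents nowhere say that p > 0.05 will be read as normalised. The hypothesis is a scientific expectation, the named tests belong to the randomised trial, and study ii is described separately. That is right. A reader might infer a committed decision rule, and the documents do not support that. What stands is narrower: no other criterion is offered, so a non-significant difference is the only basis available.

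A second reply is that any single miss rate is a scenario. This also stands. A reader might take 20% as the expected deficit and 10% as half-recovered, but 20% is only the difference to be detected. The nine-month remark describes continued improvement without a control comparison, so it does not quantify a three-month deficit. The same section calls the time of final restitution unclear and adds a later examination, which makes an unqualified claim of full recovery less likely.

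Third, the controls are matched, and an analysis that uses the matching would generally reduce the miss rates. The within-pair correlation is not given, so the reduction cannot be fixed.

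Finally, the sizing does suit the first hypothesis, reduced function at diagnosis, and study ii is ancillary: its addition is recorded as not affecting the trial's primary outcome. This limits the weight of the point but does not remove it.

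**Conclusion.** The concern holds in this form: study ii poses a normalisation question, is sized only to detect a 20% difference, and gives no criterion that could establish normalisation. If non-significance were used, a residual deficit of 5% to 20% would pass about 89% to 21% of the time at 50 v 55, and 91% to 37% at 27 v 55. These figures assume the plan's mean and SD, a two-sided unpaired t-test, no loss of participants and one measure (knee flexion at 90 degrees). They are not a forecast, because no three-month deficit is stated.

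Two stronger readings are not supported. One is that the plan will declare normalisation wrongly at some fixed rate. The other is that pooled patients are the group to test: the no-difference hypothesis covers the vitamin D arm, and the plan expects the other arm to remain impaired. The point should be addressed, but it does not bear on the trial's primary analysis.

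**What to change.** In the study ii Hypothesis and Statistics/strength calculation sections, state that:

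1. the three-month comparison is reported as a difference from controls with a 95% CI, separately for each randomised arm, and for all patients as well if the general purpose is kept;
2. a non-significant difference is not read as normalisation;
3. normalisation in knee flexion at 90 degrees is concluded only if the lower 95% confidence limit for patients minus controls lies above a pre-set margin no wider than the plan's 20% (92.6 N), and otherwise the report says that normalisation was not shown.

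The text should also say whether the vitamin D comparison uses about 50 or about 27 patients, and whether the analysis uses the matching.

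The wording costs a few sentences, but the downside must be stated. At true equality the 20% margin is met only about 79% of the time at 50 v 55 and 63% at 27 v 55. A true 10% deficit would still meet it about 28% or 21% of the time. A 10% margin could be met only about 28% or 21% of the time even at true equality, so a tighter margin makes an inconclusive result likely.

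Study ii was planned to start in August 2015 and finish within 1.5 years, and the current protocol is dated May 2017, so three-month data may already exist. If the comparison has been seen, a margin set now should be labelled post hoc; items 1 and 2 can still be adopted.

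### The control-cohort hypothesis rests a three-month vitamin D effect on two separate comparisons with controls and is not tied to the randomised comparison of the arms

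*Combined protocol and SAP*

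**What the plan says.** The section on the controlled cohort study ii), under Hypothesis, makes a two-part statement about three months after the start of anti-thyroid treatment. In the vitamin D arm, "there is no longer a difference between controls and the patients who have received vitamin D supplementation". In the other arm, "patients who have not received vitamin D supplementation continue to have reduced muscle and balance function compared to the controls".

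The Statistics/strength calculation section of study ii contains only size and power statements for detecting differences. For knee flexion at 90 degrees it assumes "463N with a standard deviation of 170 N". The target is worded "To detect a difference between groups of 20" per cent, "with a power of 0, 80", and the result is that "53 participants are required in each group". It gives no margin for the absence of a difference, no comparison of vitamin D with placebo, and no test of whether the two differences from controls differ from each other. It also does not say how many patients enter study ii.

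The randomised study (study i) covers the same outcome. Muscle and balance function is among its secondary outcome measures. The Statistical analysis plan (Original) puts the placebo versus vitamin D comparison first and uses a two-group t-test or a non-parametric equivalent for outcomes other than the primary. The final statistical analysis plan again lists a two-sample t or Wilcoxon test for continuous variables. The study ii hypothesis refers to none of this.

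**The concern.** Two inferences are built into the hypothesis, and neither is sound. The first reads a non-significant difference from controls as recovery, when it may only mean that the arm is too small to show the deficit that remains. The second reads one significant and one non-significant comparison as a difference between the arms. Two arms with the same true deficit can fall on opposite sides of 0.05 by chance.

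At stake is a report that vitamin D speeds muscle recovery when the randomised comparison of the same patients does not show it.

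**Working it through.** **Inputs.** Mean 463 N, SD 170 N, alpha 0.05, power 0.80 and a 20% difference (0.20 × 463 = 92.6 N) come from the study ii statistics section. The 55 controls come from its Population section. Fifty patients per arm comes from the sub-cohort of 100 in the study i Population size section. Two-sided testing is an assumption for study ii, taken from the 1.96 in the study i bone calculation. Sharing all 55 controls between both comparisons, a single measure and unpaired tests are also assumptions.

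**The plan's own figure.** n = 2 × SD² × (1.96 + 0.84)² / Δ² = 2 × 28,900 × 7.84 / 8,574.76 = 52.8, so 53 per group. The stated size reproduces, as a size for detecting a 20% deficit.

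**Chance of the supporting pattern with identical arms.** Let both arms have the same true deficit d.

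- Standard error of each arm-versus-control difference: 170 × √(1/55 + 1/50) = 33.2 N.
- Correlation of the two comparisons through shared controls: (1/55) / (1/55 + 1/50) = 0.476.
- Supporting pattern: Z > 1.96 for placebo (significantly reduced) and |Z| < 1.96 for vitamin D, with both Z centred at d/33.2 and correlated at 0.476 (bivariate normal).

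| Common deficit | d (N) | d/SE | An arm is called no different | Supporting pattern |
|---|---|---|---|---|
| 0% | 0 | 0 | 95% | 2.1% |
| 5% | 23.2 | 0.70 | 89% | 7.1% |
| 10% | 46.3 | 1.39 | 71% | 14.3% |
| 15% | 69.5 | 2.09 | 45% | 16.9% |
| 20% | 92.6 | 2.79 | 20% | 11.7% |

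The peak lies where each comparison has 50% power, at d = 1.96 × 33.2 ≈ 65 N (14% of 463 N). It equals approximately 1/4 − arcsin(0.476)/(2π) = 0.250 − 0.079 = 17.1%. A simulation of 100,000 trials with t-tests at 65 N gave 16.9%. In the same simulation a direct two-sided test of the arms wrongly favoured vitamin D in 2.4% (nominal 2.5%).

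**Sensitivity to the number of patients.** The study ii pulse wave velocity power of 0.94 (1 m/s, SD 1.5 m/s) fits 55 per group: 1 / (1.5 × √(2/55)) = 3.50, and Φ(3.50 − 1.96) = 0.94. That suggests about 55 patients in all, or 27–28 per arm. With 27.5 per arm the standard error is 39.7 N, the correlation is 1/3, and the peak is 0.250 − 0.054 = 19.6%, at about 78 N (17%). Simulations with 27 and 28 per arm gave 19.5% and 19.3%. At a 20% deficit the pattern then appears about 18% of the time. If each arm were compared only with its own matched controls, the correlation would be 0 and the peak 25%.

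**What a margin would do (50 per arm).** With a 20% margin, the 95% CI excludes the margin when the observed deficit is below 92.6 − 1.96 × 33.2 = 27.5 N. A fully recovered arm meets this with probability Φ(27.5/33.2) = 80%. An arm with a true 10% deficit meets it with probability Φ((27.5 − 46.3)/33.2) = 29%. With a 10% margin the limit is 46.3 − 65.1 = −18.8 N, and a fully recovered arm meets it with probability Φ(−18.8/33.2) = 29%.

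**The case against.** The strongest objection is that study ii states a hypothesis, not a test rule. Nowhere does the plan say that two tests at 0.05 will be run or that the pattern will be read as a vitamin D benefit. Muscle and balance function also covers several measures, none singled out in the hypothesis, whereas the calculation uses one. This stands. A reader might infer that the plan contains a decision rule with a 17% false-positive rate, and the documents do not support that. What they show is a claim framed as two comparisons with controls, with no other analysis specified in study ii.

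Second, a direct vitamin D versus placebo test of this outcome is already planned in study i, with sub-cohort examinations at three months. This also stands and lessens the consequence, so it would be wrong to say that the plan lacks such a test. The gap is that the study ii hypothesis does not depend on its result.

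Third, the inflation depends on the remaining deficit at three months, which the documents do not quantify. With none left, the pattern is rare. This is correct, although the hypothesis itself predicts a remaining deficit in the arm without vitamin D, so the inflated range is relevant. The number of patients and the unpaired analysis of matched controls are likewise assumptions.

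Fourth, the 53 per group fits the baseline hypothesis of reduced function in patients. Not sizing a secondary statement for equivalence is a limitation, not an error. That is accepted.

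**Conclusion.** The point holds as a gap between the study ii hypothesis and the analysis that could support it. Judged as worded, by two-sided tests at 0.05, it would appear supported with identical arms in about 2% of trials at no deficit, 7% at 5%, and 12–17% at 10–20%, against 2.5% for a direct test. These figures rest on one measure, 463 N, SD 170 N, 50 per arm and 55 shared controls. With 27–28 per arm the peak is about 19–20%. The figure of 17% is the maximum for one assumed configuration, not a property of the plan. The point concerns a secondary claim of the cohort study and does not touch the trial's primary outcome.

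**What to change.** State in study ii that the three-month vitamin D claim rests on the direct randomised vitamin D versus placebo difference in muscle and balance function, adjusted for the baseline value of the measure. Report each arm against controls with a 95% CI as descriptive, and say that a non-significant difference will not be read as normalisation. If normalisation is to be claimed, set a justified margin in advance, smaller than the 20% used for sizing, since at 20% an arm with a true 10% deficit would pass about 29% of the time.

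The cost is rewording and one model on data already collected. The claim becomes harder to make. Before baseline adjustment, the direct test has power 0.78 for a 92.6 N difference with 50 per arm, and 0.52 with 27.5 per arm. A strict margin may be out of reach at about 50 per arm: even at 20% a fully recovered arm would meet it only about 80% of the time.

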Other effect measures are calculated with t-test for two independent groups or a corresponding non-parametric test, depending on the distribution of the material. A significance level of 0.05 will be used. Primarily, data will be analyzed according to the "intention-to-treat" principle, although secondarily an "on treatment" analysis will be carried out, where the degree of compliance is corrected.

The intention-to-treat population consists of all participants who have been randomized to the study and who have received at least one dose of the study medication. In the event of missing data in the Intention-to-treat analysis, "last value carried forward" will be used. In the final protocol, there will be an account of unused or omission of inauthentic data, as well as an account of reasons for any deviations from the originally planned statistical analyses.

It is planned to carry out interim analyzes when the sub-cohort of 100 subjects (which includes mainly from Aarhus University Hospital and Regional Hospital Silkeborg) has completed the entire study program. This is to ensure that this population can be included in a data analysis which will form the basis of a PhD thesis

Study population

260 patients, men and women, with newly diagnosed GS where anti-thyroid treatment is planned. Potential study participants are recruited from hospitals in Central Denmark Region in connection with patients' attendance at the outpatient clinic.

Inclusion criteria

- Newly diagnosed Graves' disease verified by TSH below the reference range and thyroxin and/or triiodothyronine (T3 and/or T4) above the upper reference range.
- Age 18 years or older
- Elevated plasma level of thyroid stimulating immunoglobulin (TRAb)

- Planned or started (< 3 months) medical anti-thyroid treatment
- Speaks and reads Danish.
- Written consent after oral and written information

Exclusion criteria

- Daily intake of vitamin D supplements of more than 10 micrograms, which the participant wishes to continue.
- A previously diagnose of hyperthyroidism
- Planned treatment with radioactive iodine or thyroidectomy
- Chronic granulomatous disease
- Significant hypercalcemia (ionized plasma calcium $> 1.40 \text{ mmol/l}$)
- Reduced kidney function (eGFR $< 45 \text{ ml/min}$)
- Regular intake of medication with known immuno-modulating effects, including systemic glucocorticoids ($>5\text{mg/day}$ for 3 months), imurel, methotrexate, TNF α -inhibiting agents.
- Active malignant disease

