If you contact us regarding the above advertisements, you will be sent written information about the project before any informational interview.

"Forskerservice" will be requested a data file with name, address, age, and gender, and social security number for 25,200 people aged 18-80 from the Aarhus area (200 per age per gender). Every time a patient with Graves' disease is included in the intensive study cohort, a letter will be sent via e-box to 20 gender- and age-matched (+/- 2 years) people from this data extract.

The letter sent will contain a cover letter (appendix 12) as well as participant information (appendix 13) and the pamphlet "Subject's rights in a biomedical research project" (appendix 7). In the cover letter, there will be a link to an internet-based mixed response (appendix 14), in which the participant can state whether he or she is interested in participating in the survey. If interest is expressed, the participant will be asked to answer a short questionnaire regarding menopause status (women only) and exclusion criteria. The questionnaire is answered pseudo-anonymized without directly identifiable information using a username and codes in the sent covering letter. It will appear from the written information material that further information about the project can be obtained by contacting the investigator whose telephone number is given. If there is no response, information about the project will be re-sent after 1 week. If no response is obtained from the potential trial participants, a letter is sent out to another 20 people who are matched in the same way on age and gender. The above procedure is repeated if there is no response.

Interested potential participants are requested to come to an interview about the project. The participant is informed about the possibility of bringing a companion. The information interview will take place at Aarhus University Hospital and will be handled by the investigator or someone else from the project group. The conversation will take place in an undisturbed setting behind closed doors and without interruptions. Sufficient time is set aside for conducting the interview (minimum 30 min). The procedure for this information interview will follow the guidelines as stated under the randomized study i) above.

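### Study ii screens controls for metabolic, neuromuscular and other significant disease but not the patients, so the patient-control deficit and any failure to normalise may partly reflect comorbidity

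*Combined protocol and SAP*

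**What the plan says.** Under the heading for the controlled cohort study ii), the hypothesis is that "Muscle and balance function in newly diagnosed patients with Graves' disease will be reduced compared to healthy sex- and age-matched controls". At three months, supplemented patients are expected no longer to differ from controls, while unsupplemented patients are expected to remain below them. The control level is thus the yardstick for both the baseline deficit and normalisation.

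The control exclusion criteria include "Current or previous metabolic disease", "Significant other disease, including renal impairment (eGFR <60 ml/min, hypercalcemia, treatment with the glucocorticoid system" and "Known neuromuscular disorders". This list cannot also govern the patients, because "Euthyroidism" is one of its inclusion criteria.

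No separate patient criteria are given for study ii. The recruitment text ties each control to a patient in the trial's sub-cohort: "Every time a patient with Graves' disease is included in the intensive study cohort, a letter will be sent via e-box to 20" matched people. The patients therefore enter under the randomised study's criteria. There the renal item ("Reduced kidney function (eGFR") uses a cut-off of 45 ml/min, and systemic glucocorticoids are barred only above 5 mg/day for 3 months. Neuromuscular disease, metabolic disease other than previous hyperthyroidism, and other significant disease as a general category do not appear.

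Controls are matched on sex, age within 2 years and menopause status. No restriction, adjustment or sensitivity analysis for comorbidity is specified for the patient-control comparison.

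**The concern.** A person with a neuromuscular disorder or an eGFR of 50 can be a patient in study ii but cannot be a control. Such conditions can lower strength and balance for reasons unrelated to the thyroid. Removing them from one side only pushes the comparison in one direction: the baseline deficit looks larger, and some of it will not recover with anti-thyroid treatment or vitamin D. A stable comorbidity shortfall could then be read as incomplete recovery from Graves' disease.

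The size of the deficit is itself a target result. The protocol's background states that the degree of muscle weakness compared with healthy people has not been described before. The baseline bone density and pulse wave velocity comparisons share the asymmetry, though the documents offer nothing with which to size it there.

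**Working it through.** **1. Criteria side by side** (control criteria from study ii; patient criteria from the randomised study).

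| Condition | Controls | Patients |
|---|---|---|
| Neuromuscular disorder | barred | not barred |
| Metabolic disease | barred, current or previous | only previous hyperthyroidism barred |
| Other significant disease | barred generally | only listed items (e.g. active malignancy, chronic granulomatous disease) |
| eGFR (ml/min) | below 60 barred | below 45 barred |
| Glucocorticoids | treatment barred | barred only above 5 mg/day for 3 months |
| Calcium | hypercalcaemia barred | ionised calcium above 1.40 mmol/l barred |
| Alcohol or substance abuse, pregnancy | barred | barred |

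**2. The plan's own figure.** Inputs from the strength calculation for study ii: mean knee flexion 463 N, SD 170 N, difference 20%, power 0.80, significance level 0.05 (two-sided assumed).

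- Difference: 0.20 × 463 = 92.6 N.
- n per group = 2 × (1.96 + 0.84)² × 170² / 92.6² ≈ 52.9, i.e. 53. This matches the plan.
- Power at the planned 55 v 55 is 0.815.
- The stated pulse wave velocity power of 0.94 (1 m/s, SD 1.5) reproduces at 55 v 55 (0.938). At 100 v 55 it would be 0.98. So study ii is sized on 55 patients, not on the whole sub-cohort.

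**3. Size of the bias.** Let p be the share of patients with a condition barred in controls and x their proportional loss of strength. Neither is in the documents; both are assumptions.

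- False deficit b = p × x × 463 N.
- Standard error at 55 v 55 = 170 × √(2/55) = 32.4 N.
- Standard error for one treatment arm (half of 55, about 27) v 55 controls = 39.7 N.
- With no true Graves' effect, the chance of a significant result = Φ(b/SE − 1.96) + Φ(−b/SE − 1.96).

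| p | x | b (N) | Share of 92.6 N | 55 v 55 | One arm v 55 |
|---|---|---|---|---|---|
| 10% | 10% | 4.6 | 5% | 0.05 | 0.05 |
| 20% | 20% | 18.5 | 20% | 0.09 | 0.08 |
| 30% | 30% | 41.7 | 45% | 0.25 | 0.18 |

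**4. Precision after restriction.** A 30% loss leaves about 39 of 55 patients. For the 92.6 N difference, power = Φ(92.6/SE − 1.96), with SE = 170 × √(1/n₁ + 1/n₂).

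- 39 v 55: 0.74.
- 39 v 39 (matched controls also dropped): 0.67.
- One arm, about 27 v 55: 0.64; after a 30% loss, 19 v 55: 0.53.

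**The case against.** The protocol chose healthy controls deliberately, and weakness relative to healthy people is the stated unknown. That is a legitimate comparison, and study ii is ancillary to the trial. This stands, but a difference from healthy people then mixes Graves' disease with other illness, and the plan has no step to separate them.

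Several stronger readings are tempting and are not supported:

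- **That the patients are unscreened.** They are excluded for eGFR below 45, ionised calcium above 1.40 mmol/l, granulomatous disease, active malignancy, immune-modulating drugs, alcohol or substance abuse, and pregnancy. The gap is narrower than a quick reading suggests.
- **That comorbidity demonstrably explains part of the deficit.** The documents give neither its frequency nor its effect, so one can say only that it may.
- **That the bias swamps the deficit left at three months.** If the true baseline deficit were 93 N and recovery were linear over the 4-5 months mentioned in the background, 93 × (1 − 3/4) = 23 N to 93 × (1 − 3/5) = 37 N would remain. But 93 N is a detectable difference, not an observed one, and linear recovery is not stated. The midpoint bias of 18.5 N is below even 23 N.
- **That the absence of an upper age limit for patients creates an age imbalance.** Controls aged 18-80 are matched within 2 years, which largely prevents it.
- **That a sub-cohort of 100 leaves ample room to drop patients.** The stated pulse wave velocity power corresponds to 55 v 55, and normalisation is judged within each treatment arm.

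The calcium difference is weak evidence, since the safety section describes mild hypercalcaemia as frequent and transient in the toxic phase. Restriction also needs judgement, because significant other disease is undefined; classification should therefore be blind.

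**Conclusion.** The asymmetry is in the text and its likely direction is clear: it enlarges the patient-control deficit and favours a finding of non-normalisation. Its size cannot be derived from the documents. Over the assumed range it runs from negligible (about 5 N, false-significance rate near 0.05) to material (about 42 N, rate about 0.25 at 55 v 55), with 18.5 N and about 0.09 at the midpoint. These figures assume an SD of 170 N, a two-sided 5% test and no true difference.

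A reader might infer that the vitamin D result is compromised. It is not: both randomised arms enter under the same criteria, and within-patient change does not use the controls. The sample size calculation is also correct. What needs protecting is the attribution of a deficit, or of a failure to normalise, to Graves' disease. This is a worthwhile, low-cost improvement to a secondary study.

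**What to change.** Keep the all-patient comparison and prespecify beside it a like-for-like patient-control analysis at baseline and three months. Limit it to patients who at baseline would have met the control health criteria: no neuromuscular disease, no metabolic disease other than Graves' disease, no other significant disease, eGFR at least 60 ml/min and no glucocorticoid treatment. Hypercalcaemia attributed to thyrotoxicosis should not count against a patient.

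Define significant other disease in writing. Classify patients from the recorded baseline data, blind to the strength, balance, bone and pulse wave velocity results and to treatment arm. Attribute a deficit or failure to normalise to Graves' disease only if it holds in this analysis. Leave the randomised comparison unchanged.

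No new procedures are needed. The Baseline section records current and previous illness, the Biochemistry section provides creatinine, and the Data collection section covers other medical treatment from the charts. The cost is precision: a 30% loss of patients lowers knee-flexion power from about 0.81 to about 0.74, or 0.67 if matched controls are also dropped, and by more within one treatment arm. The restricted result also applies only to patients without these comorbidities, which is why the all-patient comparison should still be reported.
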